 - i) Unintentional weight loss of $\geq 10\%$ within the previous 6 months, or
 - ii) Significant fatigue (\geq Grade 2), or
 - iii) Fevers > 100.5 °F or 38.0 °C for ≥ 2 weeks, or
 - iv) Night sweats for > 1 month.
- 4) Clinically quantifiable disease burden defined as:
 - a) For Phase 1b subjects: ALC $> 5000/\mu l$ in peripheral blood.
 - b) For Phase 2 subjects: either at least 1 node ≥ 2 cm on computed tomography (CT) or magnetic resonance imaging (MRI) confirmed by the Independent Review Committee (IRC), or a bone marrow is performed at Screening and demonstrates quantifiable CLL.

- 5) Discontinuation of all cytotoxic chemotherapy and anti-CD20 antibody therapy for ≥ 4 weeks, alemtuzumab for ≥ 8 weeks, targeted therapy for ≥ 2 weeks, and investigational therapy for ≥ 3 weeks before enrollment (Phase 1b) or randomization (Phase 2). For subjects with relapsed CLL most recently treated with B-cell receptor (BCR) pathway inhibitors who, in the opinion of the investigator, will not tolerate waiting 3 weeks, a washout period of > 5 half-lives is allowed. If on a systemic corticosteroid, the dose must be stable for the prior 4 weeks.
- 6) All acute non-hematologic toxic effects of any prior antitumor therapy resolved to Grade ≤ 1 before enrollment with the exception of alopecia or neurotoxicity (Grade 1 or 2 neurotoxicity permitted).
- 7) Eastern Cooperative Oncology Group (ECOG) score of 0, 1, or 2.
- 8) Required baseline laboratory data (within 4 weeks prior to enrollment) as shown in the following table:

Organ System	Parameter	Required Value
Hematopoietic	ANC ^a	$\geq 1 \times 10^9/L$
	Platelet	$\geq 25 \times 10^9/L$
Hepatic	Serum total bilirubin	$\leq 1.5 \times ULN$ (unless elevated due to Gilbert's syndrome or hemolysis)
	Serum ALT	$\leq 2.5 \times ULN$
	Serum AST	
Renal	C_{Cr} ^b	≥ 30 mL/min
Pregnancy	β -hCG ^c	Negative
Infection	HIV	Negative HIV antibody
	HBV	Negative HBsAg and negative HBc antibody, or positive HBc antibody and negative for HBV DNA
	HCV	Negative viral RNA (if HCV antibody is positive)
	CMV	Negative viral DNA

a ANC value to be obtained in the absence of growth factors
 b As calculated by the Cockcroft-Gault formula or measured.
 c For women of child-bearing potential only; serum β -hCG must be negative during Screening and urine pregnancy test must be negative prior to the first dose of study drug.

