Decrease in leukocytes, neutrophils, thrombocytes, and haemoglobin have frequently been reported in subjects. Drug-related neutropenia was reported in 41% (15/36) of the subjects, with a worst Common Terminology Criteria for Adverse Events (CTCAE) Grade 3 or 4 in 14/36 subjects (32%). Drug-related thrombocytopenia was reported in 31% (11/36), with a worst CTCAE Grade of 3 or 4 in 8 subjects (22%). Corresponding laboratory data showed that neutrophils and thrombocytes declined immediately after the infusion. Anemia was considered drug-related in 28% of the subjects and the highest Grade was CTCAE Grade 3. A drug-related increase of alanine aminotransferase (ALT) was reported in 4 subjects (11%), and an increase of aspartate aminotransferase (AST) was reported in 5 subjects (14%). ALT and AST elevations were Grade 1 and 2 in all subjects except for 1 subject with a Grade 3 ALT elevation. The corresponding laboratory data in these subjects showed short lasting, reversible elevations of AST and/or ALT without concomitant bilirubin elevation. Prior to the next administration of BI 836826, ALT and AST had returned spontaneously to normal or pre-treatment values.

Efficacy was observed at doses ≥ 9 mg. The Overall Response Rate (ORR) was 40% (12/30 subjects); all responses were partial responses. In addition, the decline in absolute lymphocyte count (ALC) was analyzed to assess effect of BI 836826 on CLL tumor load in 25 subjects treated at doses ≥ 9 mg, who had an elevated ALC at baseline and received at least 1 full dose of BI 836826 at the respective dose tier. A decline in ALC by 50% or more as compared to baseline was observed in 80% (20/25 of the subjects) and a reduction to $< 4 \times 10^9/L$ were observed in 56% (14/25) of the subjects.

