Grade 2 (unless clinical diagnosis is established from medical history and physical examination)	Required action: See Section 5.7.2.1 for required assessments and Section 6.1.8.9 for required testing. Recommended action: See Section 5.7.2.2 for recommended evaluations. Maintain current dose level.	Delay BI 836826 until Grade ≤ 1. Thereafter, may resume at full dose.
Grade ≥ 3 (or persistent Grade 2 diarrhea or colitis without clear etiology)	Required action: Withhold idelalisib. See Section 5.7.2.1 for required assessments and Section 6.1.8.9 for required testing. Consider anti-diarrheal (eg, loperamide) and/or addition of anti-inflammatory agent (eg, sulfasalazine, budesonide). Recommended action: See Section 5.7.2.2 for recommended evaluations. At Grade ≤ 1, may resume at lower dose level ² or discontinue study drug at investigator discretion.	If diarrhea Grade ≥ 3 recurs despite interruption of idelalisib, reduce BI 836826 to 50% ³ . BI 836826 may be increased to 100% upon resolution to Grade ≤ 1 at investigator discretion.

NCI CTCAE Grade ¹	Idelalisib	BI 836826
Hepatic Adverse Events (elevations in ALT, AST)		
Grade ≤1 (ALT/AST ≤ 3 × ULN; Bilirubin ≤ 1.5xULN)	Maintain current dose and schedule.	Maintain current dose level and schedule.
Grade 2 (ALT/AST ≤ 3-5 × ULN; Bilirubin > 1.5- ≤ 3xULN)	Maintain current dose and schedule. Recommended action: Monitor ALT, AST, ALP, and bilirubin at least 1x per week until all abnormalities are Grade ≤ 1.	Delay BI 836826 until Grade ≤ 1. Thereafter resume at full dose.
Grade 3 (ALT/AST > 5-20 × ULN; Bilirubin > 3-10xULN)	Recommended action: Withhold idelalisib. Monitor ALT, AST, alkaline phosphatase (ALP), and bilirubin at least 1x per week until all abnormalities are Grade ≤1. If bilirubin abnormality was Grade <3 resume idelalisib at same dose level. If bilirubin abnormality was Grade ≥3, resume at lower dose level ² .	Withhold BI 836826. Monitor ALT/AST at least 1x per week until Grade ≤ 1. Thereafter, may resume at full dose. If ALT/AST elevation Grade ≥ 3 recurs with BI 836826 at full dose and idelalisib at reduced dose, reduce BI 836826 to 50% ³ . Upon resolution of ALT/AST to Grade ≤1 BI 836826 may be re-escalated to 100% at investigator discretion.

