5.7. Requirements and Recommendations Regarding Specific Adverse Events or Conditions

5.7.1. Transaminase Elevations

Consistent with observations in a dog toxicology study, reversible asymptomatic ALT/AST increases were observed early in the idelalisib program in phase 1 studies (101-02 and 101-07) in subjects with hematologic malignancies. Transaminase elevations generally occurred within 4 to 12 weeks of drug initiation, and resolved spontaneously over a period of 2 to 4 weeks with drug being continued for Grade 1 and 2 elevations and drug withheld for Grade 3 or 4 elevations until resolution. These early observations are consistent with the ongoing experience with idelalisib treatment and transaminase elevations are now well characterized as most frequently asymptomatic, transient and occurring within the first 3 months of treatment.

Grade 1 or 2 elevations commonly resolve despite continued idelalisib treatment and Grade 3 or 4 elevations can be managed by temporarily withholding idelalisib. Successful rechallenge after resolution at either the same or lower dose level of idelalisib has been achieved in the majority of subjects. There has been no evidence of impaired synthetic function. Close monitoring of hepatic laboratory tests during therapy is important to allow for appropriate idelalisib interruption and reinstitution so that subjects may continue with study drug treatment.

Cholangitis manifest as hyperbilirubinemia out of proportion to serum transaminase elevations has been observed. While disease-related factors, neutropenia, toxicity from prior therapies, effects of ongoing supportive care, or pre-existing cholelithiasis may have initiated such events, it is possible that idelalisib played a contributory role. In such subjects, rechallenge with idelalisib has been possible and has not been associated with other severe adverse events.

In selected subjects who experience more complicated hepatic AEs, further workup may be warranted particularly in subjects who first experience a serum ALT/AST elevation ≥12 weeks from the start of study drug therapy, who have an elevation in serum bilirubin concentration or coagulation parameters, or who have other characteristics that suggest an atypical change in transaminase values. Hepatic AEs that require additional workup should be discussed with the Gilead Sciences Medical Monitor.

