### **7.2.2. Liver-related Laboratory Evaluations**

Liver-related abnormalities after initial study drug dosing will be examined using the following laboratory test values for postbaseline measurements:

- AST: > 3 times of the upper limit of reference range (ULN)
- ALT: > 3 x ULN
- Total bilirubin: (a) > 1.5 x ULN; (b) > 2 x ULN
- ALP > 1.5 x ULN
- ALP < 2 x ULN and total bilirubin > 2 x ULN

The listing will include laboratory data from all postbaseline visits up to 30 days after the last dose of study drug. For individual laboratory tests, subjects will be counted once based on the most severe postbaseline values. For the composite endpoint, subjects will be counted once when the criteria are met at the same postbaseline visit date.

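### The only composite liver criterion in SAP 7.2.2 has no AST or ALT term, so it does not separate transaminase elevation with concurrent bilirubin elevation from isolated high bilirubin

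*SAP*

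**What the plan says.** SAP 7.2.2 (Liver-related Laboratory Evaluations) applies these criteria to postbaseline values:

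- AST > 3 x ULN
- ALT > 3 x ULN
- "Total bilirubin: (a) > 1.5 x ULN; (b) > 2 x ULN"
- ALP > 1.5 x ULN
- the composite, "ALP < 2 x ULN and total bilirubin > 2 x ULN"

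The counting rules differ. Each single test is judged on the subject's own worst postbaseline value, whenever it occurred. The composite has a timing condition: "For the composite endpoint, subjects will be counted once when the criteria are met at the same postbaseline visit date". It is the only multi-test criterion in the section. Neither document defines an analysis criterion that joins AST or ALT with bilirubin.

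The protocol describes liver findings in these places:

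- **Section 1.3.3** characterises the BI 836826 cases as "reversible elevations of AST and/or ALT without concomitant bilirubin elevation".
- **Section 5.7.1** says further workup may be warranted in more complicated hepatic events, and includes subjects "who have an elevation in serum bilirubin concentration or coagulation parameters". The same section reports cholangitis in which bilirubin rose more than the transaminases would explain, with idelalisib possibly contributing.
- **Table 5-3**, in the hepatic rows for ALT and AST elevations, conditions the idelalisib restart dose after a Grade 3 event on bilirubin: "If bilirubin abnormality was Grade ≥3, resume at lower dose level".
- **Inclusion Criterion 8** limits entry bilirubin to 1.5 x ULN, "unless elevated due to Gilbert's syndrome or hemolysis". It gives no upper limit for those exceptions.

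**The concern.** The composite is the one place where SAP 7.2.2 requires liver tests to be abnormal together on the same date. Apart from the cholangitis remark, the protocol's account of liver toxicity starts from ALT/AST and uses bilirubin as the qualifier. A reader of the liver listing would therefore reasonably expect the composite to mark that combination. As written, its result does not depend on AST or ALT at all.

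Isolated high bilirubin is also plausible in this population. The thresholds apply to postbaseline values without reference to baseline. A subject admitted under the Gilbert's syndrome or hemolysis exception with bilirubin above 2 x ULN, and normal AST, ALT and ALP, could meet the composite at any visit without a new liver event.

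Safety listings are essentially all that remains of the analysis (SAP 3 and 7.7), so the flags in them should mean what they appear to mean.

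**Working it through.** The plan gives no figure to reproduce. The check treats the composite as a logical rule.

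**Inputs, all from SAP 7.2.2:** AST and ALT threshold 3 x ULN; bilirubin thresholds 1.5 and 2 x ULN; ALP thresholds 1.5 x ULN (single test) and 2 x ULN (composite).

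**Rules**
- Written: ALP < 2 and bilirubin > 2.
- With transaminase term: (AST or ALT > 3) and bilirubin > 2 and ALP < 2.

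**Step 1: all combinations.** Three yes/no conditions (AST/ALT > 3, ALP < 2, bilirubin > 2) give 2 x 2 x 2 = 8 cells. The written rule is true in 2 of 8. Both have ALP < 2 and bilirubin > 2, and they differ only in AST/ALT status. The rule with the transaminase term is true in 1 of 8, and that cell is one of the same two. So the written rule catches everything the narrower rule catches, plus isolated high bilirubin.

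**Step 2: illustrative profiles.** Values are assumed, in x ULN, with AST taken as no higher than ALT.

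| Profile | ALT | Bilirubin | ALP | Written composite | With AST/ALT term | Single tests met |
|---|---|---|---|---|---|---|
| A | 1.0 | 2.2 | 1.0 | yes | no | bilirubin (a), (b) |
| B | 8.0 | 2.2 | 1.0 | yes | yes | ALT; bilirubin (a), (b) |
| C | 8.0 | 1.0 | 1.0 | no | no | ALT |
| D | 8.0 | 2.2 | 2.5 | no | no | ALT; bilirubin (a), (b); ALP |

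The written composite marks A and B alike (2 of 4). The rule with the transaminase term marks B only (1 of 4).

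**Step 3: do the single-test flags already supply the distinction?** They separate A from B, because only B meets ALT > 3. They do not establish timing. Take a subject with profile C at one visit and profile A at a later one. That subject meets ALT > 3, bilirubin (a) and (b), and the written composite, which is the same set as B, although the two elevations never coincided. The added rule is false at both visits (bilirubin 1.0 at the first, ALT 1.0 at the second), so it separates this subject from B.

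**Step 4: the composite lies inside bilirubin (b).** Take a grid of ALT (1, 2.5, 3.1, 8, 25), bilirubin (1, 1.8, 2.2, 3.5, 11) and ALP (1, 1.8, 2.5), giving 5 x 5 x 3 = 75 combinations. The written composite is met by 5 x 3 x 2 = 30. All 30 have bilirubin > 2, and 2 x 3 x 2 = 12 of them have ALT at or below 3. This illustrates the logic and says nothing about frequency.

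**The case against.** The case against is substantial, and most of it stands.

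- **No sensitivity is lost.** A reader might infer that the composite misses transaminase elevation with concurrent bilirubin elevation. It does not when ALP is below 2 x ULN, because every such case meets it (profile B). The weakness is one of separation only.
- **No data are lost.** The liver listing covers all postbaseline visits up to 30 days after the last dose, and SAP 7.2 lists all serum chemistry by subject and time point with abnormal values flagged. With two subjects, concurrence can be checked by reading the rows. No dose decision or test depends on the flag.
- **Bilirubin-predominant injury is a pattern the protocol names.** The cholangitis remark in Section 5.7.1 means that a flag not requiring AST or ALT > 3 x ULN has a use. This is a good reason against replacing the existing bullet. It does not make that bullet a test for the pattern, since the bullet does not compare bilirubin with transaminases.
- **Intent is unknown.** Neither document says what the composite was for or whether the AST/ALT term was left out on purpose. A reader might infer a contradiction between protocol and SAP. There is none, because the protocol defines no combined criterion for analysis, and Table 5-3 concerns dosing and uses different cut-offs (bilirubin Grade 3 starts above 3 x ULN, not 2).
- **Profile D is still not marked by either composite.** This is correct. The ALP condition is carried over from the SAP's own bullet, and D remains visible under the ALT, bilirubin and ALP single tests.

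What survives is narrow. No flag in SAP 7.2.2 identifies AST/ALT and bilirubin elevated on the same date.

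**Conclusion.** The point holds as a low-impact matter of specification. The sole composite reduces to bilirubin criterion (b) restricted to ALP below 2 x ULN, and it does not separate concurrent transaminase and bilirubin elevation from isolated high bilirubin.

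The two subjects' laboratory values are not in the documents, so the number affected is 0, 1 or 2 of 2. It is 0 if neither exceeds bilirubin 2 x ULN. The logical result needs no assumption beyond the text of SAP 7.2.2. The view that the concurrent combination deserves its own flag rests on Protocol 1.3.3, 5.7.1 and Table 5-3, not on any stated purpose of the composite.

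**What to change.** Add one bullet to SAP 7.2.2: (AST or ALT > 3 x ULN) and total bilirubin > 2 x ULN and ALP < 2 x ULN, on the same postbaseline visit date. Keep all single-test criteria. Keep the existing bilirubin/ALP bullet as a separate item, so that a bilirubin-predominant case with ALP below 2 x ULN is still flagged. Make the counting sentence plural so that the same-date rule covers both composites.

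The thresholds are the SAP's own, and all four tests are in the chemistry panel of Protocol Table 6-1, so no new data are needed and no value leaves a listing. The cost is one additional flag in the liver listing. If the SAP is already final, its Introduction provides for documenting the change in the CSR.

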### **7.3. Body Weight , Height, and Vital Signs**

A by-subject listing of vital signs will be provided by subject ID number and time point in chronological order. Body weight, height, and BMI will be included in the vital signs listing, if space permits. If not, they will be provided separately.

### **7.4. Prior and Concomitant Medications**

Medications collected at screening and during the study will be coded using the current version of the World Health Organization Drug dictionary.

#### **7.4.1. Prior Medications**

Prior medications are defined as any medications taken before a subject took the first study drug. For the purposes of analysis, any medication with a start date prior to the first dosing date of study drug will be included in the prior medication summary regardless of when the stop date is. If a partial start date is entered, the medication will be considered prior unless the month and year (if day is missing) or year (if day and month are missing) of the start date are after the first dosing date.

#### **7.4.2. Concomitant Medications**

For the purposes of analysis, any medications with a start date prior to or on the first dosing date of study drug and continued to be taken after the first dosing date, or started after the first dosing date but prior to or on the last dosing date of study drug will be considered concomitant medications. Medications started and stopped on the same day as the first dosing date or the last dosing date of study drug will also be considered concomitant. Medications with a stop date prior to the date of first dosing date of study drug or a start date after the last dosing date of study drug will be excluded from the concomitant medication summary. If a partial stop date is entered, any medication with the month and year (if day is missing) or year (if day and month are missing) prior to the date of first study drug administration will be excluded from the concomitant medication summary. If a partial start date is entered, any medication with the month and year (if day is missing) or year (if day and month are missing) after the study drug stop date will be excluded from the concomitant medication summary. Medications with completely missing start and stop dates will be considered as a concomitant medication.

All prior and concomitant medications (other than per-protocol study drugs) will be provided in a by-subject listing sorted by subject ID number and administration date in chronological order.

### **7.5. Electrocardiogram Results**

A by-subject listing for electrocardiogram (ECG) data and assessment results will be provided by subject ID number and time point in chronological order.

#### **7.5.1. QT Intervals**

The QT interval (measured in millisecond [msec]) is a measure of the time between the start of the Q wave and the end of the T wave in the heart's electrical cycle. The QT interval represents electrical depolarization and repolarization of the ventricles.

#### **7.5.2. PR and QRS Intervals**

The PR interval (measured in msec) is a measure of the time between the start of the P wave (the onset of atrial depolarization) and the beginning of the QRS complex (the onset of ventricular depolarization). The QRS interval measures the duration of the QRS complex.

## **7.6. Other Safety Measures**

Since only 2 subjects were enrolled at time of study termination, the dose limiting toxicity (DLT) will not be evaluated.

## **7.7. Changes From Protocol-Specified Safety Analyses**

Due to the early study termination, only safety-related endpoints will be listed for the subjects enrolled in the study.

## **8. PHARMACOKINETIC (PK) ANALYSES**

### **8.1. PK Sample Collection**

This study was terminated in Phase 1b based on an updated feasibility assessment in relation to changes in the CLL treatment landscape. Since only 2 subjects were enrolled at the time of study termination, PK samples will not be evaluated.

### **8.2. PK Analyses Related to Intensive PK Sampling**

Not Applicable

### **8.3. PK Analyses Related to Sparse PK Sampling**

Not Applicable

## 9. REFERENCES

## **10. SOFTWARE**

SAS® Software Version 9.4. SAS Institute Inc., Cary, NC, USA.

## 11. SAP REVISION

Revision Date (DD MMM YYYY)	Section	Summary of Revision	Reason for Revision

## 12. APPENDICES

### Appendix 1. Schedule of Assessments

#### Appendix Table 1. Study Procedures Table

*Shaded columns indicate laboratory draws only occur on these days*

Visit	Screen	Idelalisib Run-in and Combination Treatment through Week 18															
Week	-4	1	2	2	2	3	4	5	6	7	8	9	10	12	14	16	18
Study Day	-28	1	8	9		15	22		36		50		64	78	92	106	120
Visit Window	NA					± 1 day					± 3 days						
Informed Consent	X																
Medical History	X																
Medication History	X																
Physical Examination	X	X	X	X		X	X		X		X		X	X	X	X	
Vital Signs	X	X	X	X		X	X		X		X		X	X	X	X	
ECOG Performance Status	X																
12-lead ECG	X																
Chemistry & Hematology 	X	X	X	X	XXX	X	X	X	X	X	X	X	X	X	X	X	
Coagulation	X																
Urinalysis	X									X							
HBV, CMV, HCV, HIV Screening	X																
CMV monitoring 	X						X				X			X		X	
β 2 microglobulin		X															
Immune monitoring (CD4) 		X					X							X			
ADA testing 			X						X				X		X	X	
CCI																	
Investigator Assessment	X													X			
Idelalisib & PJP Prophylaxis Dispensing		X					X				X			X		X	
Idelalisib Accountability							X				X			X		X	
Idelalisib Administration 		→	→	→	→	→	→	→	→	→	→	→	→	→	→	→	
BI 836826 Administration 			10 mg	50%		50%	100%		X		X		X	X	X	X	
Adverse Events		X	X	X		X	X		X		X		X	X	X	X	
Concomitant Medication	X	X	X	X		X	X		X		X		X	X	X	X	

ALL FOOTNOTES APPEAR AT END OF PART 2

Visit	Combination Treatment and Post- Combination Treatment									30-Day Follow-up  End of Study 
Week	20	22	24	26	30	34	38	42	46	
Study Day	134	148	162	176	204	232	260	288	316	
Visit Window	± 3 days									±7 days
Informed Consent										
Medical History										
Medication History										
Physical Examination		X		X	X	X	X	X	X	X
Vital Signs		X		X	X	X	X	X	X	X
ECOG Performance Status										X
12-lead ECG				X						X
Chemistry & Hematology 	X	X	X	X	X	X	X	X	X	X
Coagulation										
Urinalysis				X						X
CMV monitoring 		X		X	X	X	X	X	X	X
β 2 microglobulin										
Immune monitoring (CD4) 		X					X		X	X
ADA testing 				X		X		X		X
CCI										
Investigator Assessment				X			X			X
Idelalisib & PJP Prophylaxis Dispensing		X		X	X	X	X	X	X	
Idelalisib Accountability		X		X	X	X	X	X	X	
Idelalisib Administration 	→		→	→	→	→	→	→	→	
BI 836826 Administration 		X		X	X	X	X	X	X	
Adverse Events		X		X	X	X	X	X	X	X
Concomitant Medication		X		X	X	X	X	X	X	X

- 1 Chemistry & hematology will be obtained a minimum of 3 times in the first week following completion of the first 50% dose of BI 836826 on Day 9; and once after the first full dose of BI 836826 on Day 22, then a minimum of weekly x 6 weeks, then prior to each BI 836826 infusion. All subjects should have blood counts monitored at least every two weeks for the first 6 months of idelalisib treatment. For subjects who develop ANC 0.5 to < 1.0 Gi/L, blood counts should be monitored at least weekly
- 2 CMV surveillance for active disease must be conducted approximately every 4 weeks throughout the course of idelalisib treatment.
- 3 Samples for immune monitoring were drawn at Baseline prior to the first dose of idelalisib. With the implementation of Amendment 4, only CD4 will be collected at the time points specified.
- 4 With the implementation of Amendment 4, PK and biomarker samples are no longer being collected and subjects are past Week 16. Samples for BI 836826 anti-drug antibody testing will be drawn at the time points indicated. For additional information see the protocol Appendix Table 2 PK and Anti-Drug Antibody Sampling and the Laboratory Manual.

■ [REDACTED]

- 6 Idelalisib is taken BID; on BI 836826 dose days the morning dose is taken in the clinic approximately 60 minutes prior to starting the BI 836826 infusion
- 7 BI 836826 given via IV infusion at the indicated time points, beginning with 10 mg and ramping up through 50% to 100% of the intended dose over 4 weeks
- 8 The 30-day Follow-up assessment will be done following last dose of BI 836826 (no later than Week 50).
